### **Potential benefits of the proposed research to the participants and others**

All assessment and services provided in these studies will be free. This particular pseudo randomization is considered for this study so as to offer the benefitting treatment to the majority of study population and will be similar to other recent studies. The treatments should help in TRD and preventing relapse. Subjects will be told if unusual information is discovered during the study that will make a difference in treatment for this or other problems. By taking part in this research subjects will help others with similar problems because this study is likely to identify how the treatment works and could also lead to development of biomarkers for monitoring treatment response.

### **Reimbursement**

Patients will be provided \$15 per hour for their participation in the study except for the infusion day, where they will be paid a total of \$100 for the day, as well as the 7 day follow-up, where they will be paid \$10 for the day. Total reimbursement for patients may go up to \$100 plus \$15x8 +\$10 = \$230.

### **Importance of the knowledge to be gained**

Research participation will help the patients in curing TRD and possibly preventing relapse. The current project aims to address this important gap by conducting the systematic investigation of ketamine effect on cortical neurophysiological function in TRD patients by employing EEG and Transcranial magnetic stimulation (TMS) based techniques. The selected medication has shown preliminary evidence of benefit in helping patients with TRD. TRD is highly prevalent and leads to devastating consequences on a personal and societal level. Further, this study will pilot new approaches to evaluating treatments that may lead to more personalized and effective treatments for TRD. The above stated risks are relatively mild in degree and procedures have been designed to minimize their probability. We believe this protocol has an extremely favorable risk/benefit ratio. The psychiatry department has an excellent track record in conducting similar controlled trials with the utmost attention to safety.

## **Data and Safety Monitoring Plan**

The principal investigator will be responsible for the Data and Safety monitoring of the study.

### **Data monitoring plan**

Data will be collected and stored as described above in Sources of Material, and analyzed with primary outcomes as described in the Statistical Plan. Trained research assistants will enter data into an existing, relational database. Allowable input values will be restricted to standardized Access entry forms so as to maintain data integrity. All observations will be double-entered to verify accuracy, with any problems detected discussed with the PI. If necessary, re-training of research assistants will be conducted. Due to the comparatively small and initial nature of the current trial, an interim data analysis is not planned.

### **Safety monitoring plan**

During screening, study applicants will undergo a complete psychological and physical exam to determine their eligibility and safety of their participation in this study, per inclusion/exclusion criteria detailed above. During the treatment phase of the study, participants will be asked about adverse events at each clinic visit and vital signs will be continuously monitored during the infusion and two hours after the infusion.

All adverse events (AEs) occurring during the course of the study will be collected, documented, and reported to the Principal Investigator. The occurrence of AEs will be assessed at baseline and each visit during the treatment phase of the study. The PI, in consultation with the co-investigators, will review any AE's as soon as they are reported. The study investigators will follow all AEs to the point of a satisfactory resolution. A study participant may have their medication discontinued or may be withdrawn from the study if the Study Physician determines it is the best decision in order to protect the safety of a participant. All AEs will be assessed to determine if they meet criteria for an SAE.

Serious adverse events (SAEs), as defined by the FDA, will be evaluated at each visit. Any SAE, whether or not related to study medication, will be reported to the IRB within 24 hours. The initial SAE report will be followed by submission of a completed SAE report within 2 days. In the event that a patient either withdraws from the study or the investigator decides to discontinue a patient due to SAE, the patient will have appropriate follow-up medical monitoring. Monitoring will continue until the problem requiring hospitalization has resolved or stabilized with no further change expected, is clearly unrelated to study medication, or results in death. Outcome of SAEs will be periodically reported to IRB.

### **Inclusion of Women**

The subjects will include males and females, ages 18-65 years old, from various race/ethnic backgrounds, as reflected in the local community in the greater Houston area.

### **Inclusion of Minorities**

Our study will include minority groups in proportions that will be representative of the ethnic/racial composition of the local community in Houston, Texas. Our projected numbers for minority enrollment are detailed in the enrollment table attached.

### **Inclusion of Children**

Children will not be included in the study. The inclusion of children at this early stage would increase substantially the number of subjects needed for the overall project. At this time, we will focus on an adult population (ages 18-65 years old), which will also allow us to limit some of the potential confounding factors to our brain imaging and neurocognitive findings. Depending on our results these investigations will be extended to children and individuals over 65 years old in future studies.

### **Prisoners and pregnant women**

We are aware of the special protections afforded to prisoners per federal regulations. We will not actively recruit people who are incarcerated to participate in this study. We do, however, acknowledge the possibility of research participants in our target population being incarcerated during the study. If an active participant is incarcerated,

for an extended period of time, disenrollment from the study will be necessary. No research interaction or intervention will take place until an incarcerated participant is released from jail. Finally, neither pregnant woman nor neonates will be enrolled in this study.

### **Power Analysis**

Sample size justification: For the current proposal, our power calculation is based on our prior data on ASSR (Komek K et. al 2012) after pharmacological manipulation with effect size estimate of 0.9 and is guided by a previous study which used intravenous antidepressant clomipramine in TRD patients and found decreased motor excitability (increased RMT)(Minelli A et.al 2010) with large effect size estimate of Cohen's  $d = 1.2$ . For this project proposal, even if we assume a lower effect size of  $d=0.9$ , assuming a two-sided  $\alpha < 0.05$ , a sample of  $N=15$ , randomized in a cross-over design, participants provides 95% power to detect a difference between the two groups. Our sample size of 20 subjects would be sufficient event at attrition of 20%.

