## **Study Design and Procedure**

We will employ an open-label study in which the infusion session, the enrolled TRD patients will receive low dose Ketamine (0.5 mg/kg) over 40 minutes as previous studies [58].

The overall study design is described in Figure1 above.

**Ketamine infusion:** We will use slow infusions of ketamine over a time period of 40 minutes. Study drug will be provided in syringes, containing clear solutions of 1 ml of (0.5mg/kg) ketamine. The dosage will be calculated using the patient's weight in kilograms. For dosing purposes, 0.5-0.9 round up to the next dose and from .01-0.49, we will round down to the lower dose. An ACLS psychiatrist ([name]) will monitor the patient at HCPC. The administration of ketamine will be initiated by the anesthesiologist. The anesthesiologist will be present during the ketamine administration (40 minutes) and post-procedure (until patient is awake and anesthesiologist deems patient is clinically stable). The infusions will be conducted in our hospital during the mornings in a room set specially for this study. During the infusion, patients will be asked constantly about "how they feel" and will receive constant attendance from a psychiatric nurse and the attending ACLS- trained psychiatrist. ECG and pulse oximetry monitoring will be maintained throughout the infusions to check for hemodynamic changes.

After completion of each 40 minute infusion, patients will rest for 2-4 hours under observation of the clinical nurse before being discharged to a responsible adult who will accompany the patient home after completing study tasks. Standard blood sample measurements may occur before the infusion day. All participants will undergo urine drug tests before each infusion. During the course of infusions, patients will receive treatment-as-usual from their primary psychiatrists as would be the case in a traditional therapeutic setting. There will be no changes in medication regimen throughout the 2-week trial. Participants will be provided with a contact card directing them to the nearest ER/physician in case of emergency. We will make it clear to the patient that all of the study procedures are optional at patients' and the PIs discretion.

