
**OPTIONAL: ASSR/EEG paradigm:** Task - Patients will wear ER-3A insert earphones (Etymotic Research, Elks Grove, IL, USA) for auditory stimuli and will be seated ~80 cm from an LCD computer monitor used to present visual stimuli. All stimuli are presented using E-Prime software (Psychological Software Tools, Pittsburgh, PA, USA). Click trains of 500-ms duration will be presented binaurally at  $65 \pm 5$  dB. The click train repetition frequencies will be 40 Hz and presented in the context of an auditory oddball paradigm to ensure participant attention to the stimuli. Standard stimuli will be click trains with individual clicks being 1-kHz carrier frequency whereas Oddball stimuli will be click trains with clicks of 2-kHz carrier frequency. During click train presentation and for 200 ms after click train cessation, the screen remained blank (black). Participants will be then prompted by the appearance of a central fixation cross to respond by button press with either their left index finger for Standard stimuli (110 trials per block) or their right index finger for Oddball stimuli (10 trials per block). Behavioral analyses will be conducted to confirm attention to task but only correct Standard trials will be submitted for EEG analyses.

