### Summary

We will pre-screen potential participants over the phone to minimize the invitation to non-eligible participants. During the screening visit, we will screen patients for eligibility. Patients will then arrive for their study Day # 2(Baseline), when they will get blood draws (optional), complete questionnaires and undergo TMS-EEG. Patients will come to our inpatient psychiatric hospital facility on the another day (Day # 3) , where they will be given ketamine by the study nurse. During the infusion, patients will be asked constantly about "how they feel" and will be monitored continuously from psychiatric nurse and the attending Anesthesiologist. EKG and pulse-oximetry will be monitored throughout the procedure to check for hemodynamic changes. After the completion of 40 min infusion, patients will rest for two – four hours under the observation of clinical nurse and, reassessed again by psychiatrists at 2 hours after infusion. Patients may be undergoing EEG/ASSR at 10minutes, 40 minutes and at 4 hours after infusion and blood tests after infusion(40 minutes) and 2-4 hours after infusion. Patient will then

have undergo TMS-EEG & EMG at 4 hours. Patient will be discharged to a responsible adult who will accompany the patient home. Patients will be invited again for day #4 (24 hours after infusion), where they will have to complete TMS-EEG & EMG, EEG/ASSR(optional) and blood tests(optional). They will be invited again for just TMS 7 days after infusion. Patients may be contacted every day after the infusion by telephone to check on their physical and mood status and will be scheduled for a clinical visit with the psychiatrists on days 1, 4, and 7 for a follow up assessment of mental state.

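### The power calculation is based on ASSR, but ASSR is optional and the 20-patient sample size makes no allowance for completers who decline it

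*Combined protocol and SAP*

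**What the plan says.** The Power Analysis section states that "our power calculation is based on our prior data on ASSR", with an effect size of 0.9. It adds a second source, a study of an intravenous antidepressant in treatment-resistant patients that reported reduced motor excitability with d = 1.2. It then adopts 0.9 as the lower of the two and claims 95% power with N = 15 at a two-sided 5% level. It ends: "Our sample size of 20 subjects would be sufficient event at attrition of 20" (a percentage). It does not name the outcome that the 15 patients must supply.

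The status of ASSR is set elsewhere:

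- Study Design and Procedure introduces it as "OPTIONAL: ASSR/EEG paradigm: Task - Patients will wear ER-3A insert earphones".
- The Summary of visits says for the infusion day: "Patients may be undergoing EEG/ASSR at 10minutes, 40 minutes and at 4 hours after infusion". It marks ASSR optional again at 24 hours and does not mention it in the text for the baseline visit.
- Objectives labels the ASSR aim exploratory, although the same paragraph calls it the study's first goal. The main objective given there is cortical excitability by TMS-EEG.
- Study Design and Procedure also tells patients that "all of the study procedures are optional at patients' and the PIs discretion".

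The Statistics section plans paired t tests for change between two time-points.

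**The concern.** Attrition means leaving the study. A patient who stays but does not have an optional measurement is a separate loss, and the sizing sets that loss to zero. The 20% allowance leaves a margin of one patient over 15, so two completers without paired ASSR data use it up.

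What is at stake is how an ASSR result would be read. If only ten or twelve patients have usable pre- and post-infusion recordings, a null finding would stand beside a protocol that claims 95% power, although power for that comparison would be well below the claim.

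**Working it through.** **Inputs.** From Power Analysis: effect size 0.9, N = 15, two-sided 5%, stated power 95%, 20 enrolled, 20% attrition, and d = 1.2 for resting motor threshold (RMT). From Statistics: a paired t test for change. The ASSR uptake rate is not in the documents, so a range is shown. The effect of 0.9 is taken as the mean within-patient change divided by the standard deviation of the changes; the documents do not say how it was standardised.

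**Step 1: the plan's own figure.** By the normal approximation, power = Φ(d√n − 1.96). With d = 0.9 and n = 15, this is Φ(3.486 − 1.960) = Φ(1.526) = 93.6%, close to the stated 95%. The exact two-sided paired t test uses the noncentral t distribution with n − 1 degrees of freedom and noncentrality d√n. At n = 15 the critical value is 2.145, the noncentrality is 3.486 and power is 89.9%. The exact test first reaches 95% at n = 19 (96.0%). So the printed figure is roughly a normal-approximation result, and the planned test gives about 5 points less.

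**Step 2: the attrition allowance.** 15 / 0.8 = 18.75, so 19 enrolled would be needed and 20 covers it. 20 × 0.8 = 16 completers.

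**Step 3: uptake needed to reach the plan's own 15.** With the full 20% lost, 15/16 = 93.75% of completers. With no losses, 15/20 = 75%.

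**Step 4: power by number with paired ASSR data**, d = 0.9, two-sided 5%:

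| Patients with paired data | Share of 16 completers | Exact paired t | Normal approximation |
|---|---|---|---|
| 16 | 100% | 91.9% | 95.0% |
| 15 | 94% | 89.9% | 93.6% |
| 14 | 88% | 87.5% | 92.0% |
| 12 | 75% | 81.0% | 87.7% |
| 10 | 63% | 71.7% | 81.2% |
| 8 | 50% | 59.1% | 72.1% |

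Going from 15 to 14 costs 2.4 points by the exact test (89.9 − 87.5). Going from 16 to 12 costs 10.9 points (91.9 − 81.0).

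**Step 5: the second effect size.** At d = 1.2 the exact paired t test gives 94.7% with 11 patients and 99.1% with 15.

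**Step 6: sensitivity to the standardiser.** If 0.9 were expressed in units of the between-patient standard deviation, the within-patient effect would be 0.9/√(2(1 − ρ)), where ρ is the correlation between the two measurements. At n = 15 the exact power would be 78.2% for ρ = 0.3, 89.9% for ρ = 0.5 and 95.1% for ρ = 0.6. The level of the table depends on this reading. That power falls as uptake falls does not.

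**The case against.** The strongest reply is that the sample size does not rest on ASSR alone. The Power Analysis says the calculation is also guided by the motor-threshold study, and 0.9 can be read as a cautious value for the neurophysiology as a whole. Objectives puts TMS-EEG excitability first and labels ASSR exploratory. At d = 1.2, 11 patients give 94.7%. This stands, and it rules out two stronger readings.

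- A reader might infer that the study's power fails unless about 94% of completers have ASSR. The documents do not support that. The section names no powered outcome. The 94% applies only if the full 20% are lost. It is not a pass/fail point either: with the planned test, 95% is missed even at full uptake (91.9% with 16), and power falls gradually below that.
- A reader might infer that sizing on RMT removes the problem. It does not, because TMS is also placed under an optional heading in Neurophysiological assessment, the EMG recordings that RMT needs are only described as possible, and all procedures are called optional. The Summary nevertheless has patients undergo TMS-EEG.

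It is also true that no uptake rate is given and that the design figure is not shown, so ASSR may be scheduled at baseline there. Objectives reports a standardised effect of 0.66 for an earlier ASSR drug study, but the documents do not show whether that study is the source of the 0.9, so no conclusion is drawn from it.

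What the reply leaves untouched is the wording: the calculation is said to be based on ASSR, and sufficiency is claimed without allowing for non-uptake of it. If ASSR is only exploratory, that is a further reason not to print a 95% claim derived from it.

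**Conclusion.** The concern holds in a limited form. For ASSR, the measure the power calculation is said to be based on, 95% power and sufficiency at 20% attrition are not secured by a plan that leaves ASSR optional and allows nothing for non-uptake. With 8 to 16 patients supplying paired data, power at an effect of 0.9 runs from 59.1% to 91.9% with the planned two-sided paired t test. Where in that range the study would fall cannot be determined from the documents.

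This rests on reading 0.9 as a within-patient standardised effect and on an assumed range of uptake. It does not show that the study is too small for its main TMS-EEG objective.

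**What to change.** In Power Analysis:

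- Name the outcome being powered.
- Replace the 95% and sufficiency statements with power by the two-sided paired t test at d = 0.9, over the range of patients expected to have paired data on that outcome. For ASSR, n = 8 to 16 as tabulated above would serve.
- Label ASSR as exploratory and attach no 95% power claim to it.

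In Statistics, require the number of patients with paired data to be reported beside every ASSR result.

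If RMT is named as the sizing outcome, apply the same allowance to it. The optional heading over TMS, the conditional wording on EMG recordings and the statement that all procedures are optional must then be reconciled with the Summary, where patients undergo TMS-EEG.

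The cost is a rewritten paragraph, one reporting line and a less favourable stated power. No extra patients or procedures are needed. Making ASSR compulsory would also close the gap, but it would add required recordings on the infusion day and at 24 hours, so it is not proposed here.

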### **Statistics**

Normality assumptions for continuous variables will be examined. Where appropriate, outliers will be winsorised and log, square root or reciprocal transformations applied to achieve normality if appropriate. If normality cannot not been achieved, either untransformed or dichotomized scores were used. Baseline characteristics will be compared between responders and non-responders with the Mann-Whitney U test for continuous variables and the chi-square test for categorical variables. Changes between two time-points for continuous variables were tested with paired t tests, and associations between continuous variables will be quantified with the Spearman correlation coefficient. Random effects models will be performed to quantify changes in clinical score and its component items over time and to compare temporal differences between eventual responders and non-responders. Splines will be used to determine differences in the pattern of response over time among all patients and to identify the time at which there was no additional improvement in depressive symptoms. Additionally, the relationship between response status between baseline and end of study calculating sensitivity, specificity, and positive and negative predictive values will be reported. Time to relapse for patients who met response criteria at end point will be estimated with the Kaplan-Meier method. Analyses will be performed with IBM SPSS Statistics (version 19; SPSS, Chicago, Illinois) and SAS (version 9.2; SAS, Cary, North Carolina).

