**OPTIONAL: Blood Tests:**

**Gene Expression and Methylation:** The study aims to identify alterations in gene expression and methylation markers induced by the ex vivo treatment of peripheral blood mononuclear cells from symptomatic patients with treatment-resistant depression with ketamine and assess their correlations with clinical response (as measured by the reduction in the Hamilton Depression Rating Scale - HDRS). For that end blood samples will be collected from all subjects immediately before the first administration of ketamine, and peripheral blood mononuclear cells will be isolated with Ficoll-Paque®, according to the manufacturer's instructions. Cell will then be re-suspended in RPMI and plated at  $4 \times 10^5/cm^2$ . After recovery for 6 hours, cells will be treated with ketamine or vehicle. RNA and DNA samples will be isolated from peripheral blood mononuclear cells immediately after treatment (2 hours) and interrogated by RNA-sequencing (Ion Proton, Thermo Fisher) and the Infinium MethylationEPIC kit

(Illumina), respectively, according to the manufacturer's instructions. The reduction in the HDRS scores from baseline to post treatment will then be correlated with the alterations in the markers from both analyses, and the markers that show the strongest correlations with the reduction in HDRS will be selected. Moreover, expression and methylation markers will be compared between responsive and non-responsive patients. This will lead to the identification of a 'treatment response biosignature' incorporating information from gene expression and DNA methylation that can predict the response to ketamine in patients. **BDNF:** Ketamine and metabolites levels will be measured at baseline, 40 mins, 2-4 hours and 24 hours after ketamine infusion and serum BDNF tests will be performed at baseline (before each infusion), 2-4 hours and 24 hours after each infusion. Samples will be stored at Behavioral and Biomedical Sciences Building (BBSB) for analysis. BDNF concentrations were quantitatively determined by enzyme-linked immunosorbent assay (ELISA). A trained personnel will collect up to a **total** of 10 8 cc tubes (about 5.4 tablespoons) of blood from one subject in all the visits combined. A maximum of 4 8 cc tubes of blood (2.5 tablespoons) will be drawn per day from an individual.

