7. **Young Mania Rating Scale (YMRS):** This is a well-established clinical severity rating scale for manic symptoms that has adequate inter-rater reliability and internal consistency (Young et al., 1978). Frequency: Before the start of the study and at 4 hours, 24 hours and 7 days after infusion. (Changed based on the PI).
8. **Positive and Negative Affect Schedule (PANAS):** the PANAS comprises two mood scales, one that measures positive affect (PA) and the other which measures negative affect (NA). Used as a psychometric scale, the PANAS can show relations between positive and negative affect with personality stats and traits. Ten descriptors are used for each PA scale and NA to define their meanings. Participants in the PANAS are required to respond to a 20-item test using 5-point scale that ranges from very slightly or not at all (1) to extremely (5). This scale may be administered prior to and following each infusion to assess acute changes in mood. Frequency: Before the start of the study and at 4 hours, 24 hours and 7 days after infusion. (Changed based on the PI).
9. **The World Health Organization Quality of Life (WHOQOL)-Brief :** this scale is patient-reported and measures the degree of enjoyment and satisfaction experienced by subjects in various areas of daily functioning (*Endicott*

*et al.*, 1993). Frequency: Before the start of the study and at 4 hours and 24 hours after infusion. (Changed based on the PI).

**10. Hamilton Depression Rating Scale (HDRS):** a multiple item questionnaire used to provide an indication of depression, and as a guide to evaluate recovery. Frequency: Before the start of the study and at 4 hours, 24 hours and 7 days after infusion. (Changed based on the PI).

**11. Hollingshead Socioeconomic Status:** This scale is patient-reported and indication of socioeconomic status. Frequency: At the discretion of the PI.

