### **Study Population**

We will enroll 20 patients with Treatment Resistant Depression (TRD) in this study. Participants will be male and female adults, aged 18-60 years, who meet the criteria for TRD. Participants will be recruited without regard to race, religion or ethnicity. Children will NOT be included in this research. Children younger than 18 are excluded as the incidence of TRD is relatively small in individuals less than 18 years old and because the safety and efficacy of the proposed study medication and treatment should be established in adults first, before conducting this type of treatment research in children. No other special classes of vulnerable individuals will be included. Participants will be recruited through flyers and clinic referrals in the Houston area.

We anticipate recruiting equal numbers of male and female patient subjects. Men and women of all ethnic backgrounds will be recruited to participate. It is anticipated that the subject demographic profile will closely mirror the larger population of individuals with TRD from which they are recruited. We will do so by distributing flyers in neighborhoods known to have a high minority population.

Selection Criteria for individuals:

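### The only named analysis of baseline characteristics against outcome dichotomises response in 16 to 20 patients; a baseline-adjusted continuous analysis should lead, with the split kept as description

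*Combined protocol and SAP*

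**What the plan says.** The Statistics section states: "Baseline characteristics will be compared between responders and non-responders with the Mann-Whitney U test for continuous variables". Categorical characteristics get a chi-square test. Two other sentences in that section bear on the point:

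- "associations between continuous variables will be quantified with the Spearman correlation coefficient". No variable pairs are named.
- "Random effects models will be performed to quantify changes in clinical score and its component items over time". The between-patient contrast attached to these models is again eventual responders against non-responders.

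The supplied text gives no criterion for response, and no time point at which it is judged for this comparison.

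The continuous outcome is recorded. The Clinical assessment section schedules HDRS "Before the start of the study and at 4 hours, 24 hours and 7 days after infusion", and MADRS has the same schedule.

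The optional blood-test section treats its markers differently. It first says "The reduction in the HDRS scores from baseline to post treatment will then be correlated with the alterations in the markers", and selects markers on the strength of those correlations. It then adds that "expression and methylation markers will be compared between responsive and non-responsive patients".

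On numbers: "We will enroll 20 patients with Treatment Resistant Depression (TRD) in this study", and "Our sample size of 20 subjects would be sufficient event at attrition of 20" per cent, which leaves 20 × 0.8 = 16 evaluable.

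**The concern.** Improvement is measured on a scale, yet the one analysis assigned to baseline characteristics reduces it to two categories. Two patients just either side of the cut count as opposites, while a patient just above it counts the same as one who remits fully. With 16 to 20 patients there is little information to spare, and the cut itself is unspecified, so the result also depends on a choice not yet made.

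The other methods listed do not clearly fill the gap. The Spearman sentence does not say that baseline characteristics will be related to change in depression score. It cannot serve a characteristic such as sex, and it leaves baseline severity unadjusted. The random effects models compare patients by the same split.

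Markers of response are part of the protocol's stated purpose (General Information, the biomarker background section, Objectives). What is at stake is power to detect a baseline predictor from data already collected, and clarity about which result would count.

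**Working it through.** **The plan's own power figure.** The Power Analysis states 95% power at N = 15, d = 0.9, two-sided 5%. Treating d as a within-patient standardised difference, the normal approximation gives Φ(0.9 × √15 − 1.96) = Φ(3.486 − 1.96) = Φ(1.526) = 93.6%. A one-sided paired t test gives 95.2% and an exact two-sided paired t test 90.0%. So 95% is roughly reproducible, but it concerns the neurophysiological change. No power is stated for the responder comparison, and no predictor–outcome correlation is given. The correlations below are therefore assumptions, shown as a range.

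**Inputs.** n = 16 and 20 (Study Population; Power Analysis). Response proportions from Background Information: 64% on ketamine in the cited two-site trial, up to 35% at 7 days in another cited study, and 28% on midazolam as a low extreme; 45% and 50% were added as intermediate values. Two-sided 5% level.

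**Efficiency kept by the split.** If predictor and improvement are bivariate normal and a proportion p respond, splitting at cut z multiplies the squared correlation by φ(z)²/[p(1 − p)]:

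- p = 0.35: 0.3704²/0.2275 = 0.1372/0.2275 = 0.60
- p = 0.45: 0.3958²/0.2475 = 0.1567/0.2475 = 0.63
- p = 0.64: 0.3741²/0.2304 = 0.1400/0.2304 = 0.61

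An even split gives 0.64, and p = 0.28 gives 0.56. At 0.60, 16 patients carry about the information of 16 × 0.60 = 9.6.

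**Hand check at correlation 0.5, n = 16, p = 0.35.** Fisher's approximation for the continuous analysis: atanh(0.5) × √13 − 1.96 = 0.5493 × 3.606 − 1.96 = 0.02, power about 51%. After the split the correlation is 0.5 × √0.603 = 0.388, and 0.4098 × 3.606 − 1.96 = −0.48, power about 31%.

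**Simulation.** 20,000 runs per cell; ranges are over response proportions of 28 to 64%. Power in %, losses in points.

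| n | Assumed correlation | Exact Mann-Whitney on split | Spearman on change | Linear on change | Loss v Spearman | Loss v linear |
|---|---|---|---|---|---|---|
| 16 | 0.2 | 6.5–7.5 | 10.4–10.7 | 11.2–11.7 | 2.9–4.2 | 3.7–4.8 |
| 16 | 0.3 | 10.6–12.6 | 17.7–18.9 | 20.2–21.1 | 5.8–7.2 | 7.8–9.7 |
| 16 | 0.4 | 16.4–19.7 | 29.8–30.4 | 34.3–35.1 | 10.5–13.5 | 15.1–18.0 |
| 16 | 0.5 | 24.9–30.3 | 46.0–46.5 | 53.0–53.3 | 15.8–21.6 | 22.8–28.1 |
| 16 | 0.6 | 36.8–44.6 | 64.9–65.5 | 72.8–73.5 | 20.6–28.3 | 28.8–36.0 |
| 16 | 0.7 | 52.6–62.4 | 83.1–84.0 | 89.5–90.1 | 20.9–30.9 | 27.4–37.1 |
| 20 | 0.2 | 8.5–9.4 | 12.0–12.3 | 13.0–13.6 | 3.0–3.8 | 4.2–4.9 |
| 20 | 0.3 | 13.8–15.8 | 22.6–22.9 | 25.4–25.6 | 7.0–9.0 | 9.7–11.6 |
| 20 | 0.4 | 21.9–25.9 | 37.6–38.2 | 42.8–43.5 | 12.3–15.7 | 17.6–20.9 |
| 20 | 0.5 | 34.3–39.4 | 56.5–57.3 | 63.7–64.4 | 17.1–23.0 | 24.5–29.9 |
| 20 | 0.6 | 49.0–56.9 | 76.5–76.9 | 83.2–83.7 | 19.9–27.6 | 26.6–34.6 |
| 20 | 0.7 | 66.5–76.2 | 91.4–92.1 | 95.4–95.8 | 15.9–25.2 | 19.6–28.9 |

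With the large-sample Mann-Whitney test, the loss against Spearman at 0.5 to 0.7 is 15.0–29.8 points, so 15 to 31 covers both forms. At zero correlation, rejection rates were 3.9–4.6% (exact Mann-Whitney), 4.9–5.2% (Spearman) and 4.8–5.0% (linear). The gain does not come from a liberal test.

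**Value of baseline adjustment.** An HDRS-like simulation assumed baseline mean 22 and SD 4, follow-up SD 6, correlation between the two of 0.4, response as a 50% reduction, n = 16 and effect 0.5. The split had 36–37% power, Spearman on change 50–51%, and follow-up adjusted for baseline 58–60%.

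**Categorical characteristics.** Under HDRS assumptions of the same kind and a 6-point group difference, uncorrected chi-square at n = 16 had 7.1% type I error and 46% power, against 49% for the adjusted model. At n = 20 the figures were 44% and 60%. This is less clear-cut, so the size of the point rests on continuous characteristics.

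**The case against.** The strongest reply has four parts.

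1. *The comparison may be only a descriptive table.* The plan says the characteristics will be compared and does not call this a search for predictors. That is fair. But it names inferential tests without labelling them descriptive, and if description was meant, baseline characteristics have no named outcome analysis at all. The same edit answers both cases.

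2. *The plan already uses the continuous outcome.* A reader might infer that it ignores continuous change altogether, or that the blood-marker section has the same defect. The documents do not support either reading. Spearman is listed for continuous variables in general, random effects models describe the score over time, and the marker section correlates continuous HDRS reduction first and adds the split afterwards. Many of the stated aims concern post-infusion or ex vivo markers, which those methods can serve. What stands is narrower: nothing assigns a continuous-outcome analysis to baseline characteristics.

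3. *The size is assumption-driven.* A reader might quote a flat loss of 15 to 30 points, or say the split throws away most of the information. Neither holds. The flat figure needs a correlation of about 0.5 to 0.7, which no section supplies, and at response proportions of 35 to 64% the split keeps more than half the efficiency.

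4. *The outcome may not be normal.* With two latent groups (predictor shifted 1.2 SD, outcomes 3 to 4 SD apart, cut midway, 35–64% responders, 3,000 runs per cell), power at n = 16 was 34–48% for the split, 32–39% for Spearman and 37–47% for the linear test. At n = 20 it was 45–61%, 39–49% and 44–57%. At 2 SD separation the split lost only about 2 to 6 points. This too is an assumption, but it shows that the loss is not guaranteed.

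**Conclusion.** The point holds in a limited form. For baseline characteristics the plan names only a responder split, on an undefined criterion, although a continuous outcome is recorded. Under a roughly bivariate normal predictor and improvement, the split costs about 3–4 points of power against Spearman at a correlation of 0.2, 6–9 at 0.3, 11–16 at 0.4 and 15–31 at 0.5–0.7, at n = 16 to 20. Clearly bimodal response could remove the loss.

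The change would not make the trial well powered for moderate predictors. At a correlation of 0.5, Spearman reaches only about 46% (n = 16) to 57% (n = 20), and 80% needs a correlation of about 0.6 to 0.7. So a remark that the split would more often miss than find a real predictor does not separate the methods: at n = 16 and correlation 0.5 it is true of Spearman too. The case for change is that the continuous analysis uses information already collected, adjusts for severity, handles both types of characteristic and does not depend on an unstated cut.

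**What to change.** In the Statistics section, make the lead analysis of each baseline characteristic a linear model of follow-up HDRS on baseline HDRS plus that characteristic. State one lead time point in advance and treat the others as secondary, so that several follow-ups do not compete. Report the slope or group difference with a 95% interval, and use a rank-based version if residuals are clearly non-normal. Keep the responder/non-responder comparison, labelled as descriptive, and state the response criterion it uses.

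In the blood-test section, it is enough to say that the correlation with continuous HDRS reduction leads and that the responder comparison is descriptive.

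The cost is a few sentences in the plan and a few lines of code. No extra patients, visits or measurements are needed.
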